8.3.3. Physical Examination

The PI or appointed designee is responsible for performing the PE. Whenever possible, the same individual will perform all PEs for each participant.

A complete PE will be performed at Screening and Day 64/EWV. This examination will include a review of general appearance, head/eyes/ears/nose/throat, respiratory system, cardiovascular system, gastrointestinal system, dermatological system, lymphatic/hematological system, musculoskeletal system, neurological system, metabolic/endocrine system, and other observations. Note that a genitourinary review is not required for the PE unless clinically indicated.

Symptom-directed PEs, a targeted examination of specific body systems based on the participant's complaint(s), are to be conducted prior to vaccination on Days 1, 15, and 29 and also during unscheduled visits occurring before Day 64.

Abnormal PE findings are to be recorded as signs and symptoms on the Medical History eCRF if presenting before the vaccination on Day 1, and as AEs after Day 1 postvaccination if new or

increased in severity/frequency following vaccination. As toxicity grading is being used in this study to record AE severity (refer to [Section 9.2.1](#)), the PI or designee will assess the severity of abnormal PE findings recorded on the AE eCRF according to [Table 8](#), which has grading options for some specific clinical symptoms, as well as a generic grading criteria for “illness or clinical AE” that will be used otherwise. Physical examination abnormalities are not to be separately reported as AEs if the PE abnormality is part of a symptom complex that is already reported as an AE. Abnormal PE findings may trigger individual participant or study halting rules (refer to [Section 7](#)).

8.3.4. Vital Signs

Vital signs including systolic and diastolic blood pressure (sitting), heart rate, respiration rate, and temperature will be obtained at Screening and each subsequent clinic visit through Day 64/EWV, including unscheduled visits occurring before Day 64. Height and weight will only be recorded at Screening. On vaccination days (Days 1, 15, and 29), vital signs will be assessed prior to vaccination and at 30 ± 5 minutes postvaccination.

The PI or designee will assess vital sign results against toxicity grade criteria (Grade 1=mild through Grade 4=potentially life-threatening) according to the FDA Guidance for Industry: *Toxicity Grading Scale for Healthy Adult and Adolescent Volunteers Enrolled in Preventive Vaccine Clinical Trials* {[CBER, 2007](#)} – refer to [Table 8](#), with grading for oral temperature (fever), heart rate (tachycardia, bradycardia), blood pressure (hypertension, hypotension), and respiratory rate. This grading – assessing severity – will aid in the evaluation of abnormalities and their reporting, if applicable, as AEs.

Any vital sign abnormalities may be followed up with repeat testing. Grade 3 or higher vital signs will be repeated twice to verify that the severity is a Grade 3 or higher. If two of the three assessments are Grade 3 or higher, the vital sign will be reported as a Grade 3 or higher abnormality. All Grade 3 or higher vital sign abnormalities and those vital sign abnormalities determined by the PI or designee to be a clinically significant change from baseline for that participant will be recorded as AEs. As toxicity grading is being used in this study to evaluate and record AE severity (refer to [Section 9.2.1](#)), the vital sign toxicity grade is to be assigned as the AE toxicity grade when reporting on the AE eCRF. Vital sign abnormalities are not to be separately reported as AEs if the abnormality is part of a symptom complex that is already reported as an AE. Vital sign abnormalities may trigger individual participant or study halting rules (refer to [Section 7](#)).

8.3.5. Other Safety Assessments

8.3.5.1. E-Diary Reactogenicity

Reactogenicity (solicited systemic and injection site reactions) will be monitored by the site for 30 minutes after vaccination and thereafter assessed daily by the participants using e-diaries, starting on the evening after each vaccination, for at least seven days. Participants who do not have or don't want to use their personal electronics to access the web-enabled e-diary will be provided a hand-held device for purposes of this study, along with pre-paid return packaging to enable its return at the conclusion of all e-diary entries. Participants will also receive instructions on e-diary completion and be provided with an oral thermometer and injection site reaction

measurement tool on Day 1. Failure of a participant to comply with e-diary entry requirements will prompt compliance alerts being issued to the participant and to the clinical site, for site staff to follow up the noncompliance with the individual.

In the participant e-diary, information will be solicited on the following injection site reactions: warmth, tenderness, itching, pain, arm motion limitation, redness, induration, swelling, and bruising. In addition, information will be solicited on the following systemic reactions: tiredness, muscle ache, headache, and fever (oral temperature). The participant will be prompted to grade the severity of each reaction according to the instructions provided [eg, Grade 0 (Absent) = symptom not present; Grade 1 (Mild) = symptom present but does not interfere with activities of daily living; Grade 2 (Moderate) = symptom causes some interference with activities of daily living; Grade 3 (Severe) = symptom prevents activities of daily living or requires treatment)]. Participants will also be asked to respond (yes/no) if they have taken pain/fever medications such as acetaminophen, aspirin, and nonsteroidal anti-inflammatory drugs (NSAIDs; eg, ibuprofen) or other medication in the past 24 hours. Participants will be directed to not take these types of medications 24 hours before or after vaccinations (refer to [Table 4](#)). Use of such medications reported in the e-diary must be confirmed with the participant and recorded in the eCRF (refer to [Section 6.5](#)). Investigational site staff will review participant e-diary entries on a routinely basis (starting with the day following vaccinations) to assess compliance, need for re-instruction and evaluation against individual participant and study halting rules. On Days 15 and 29 (also the EWV if falling within a window for e-diary entry), the investigational site staff will review e-diary entries with the participant.

If injection site or systemic reactions continue beyond seven days, participants will be prompted to continue e-diary entries until they are symptom-free for two consecutive days. For any type of reactogenicity persisting two weeks or more, the PI or designee will evaluate the reaction at the next scheduled visit and/or determine based on the nature and severity if a more immediate unscheduled follow-up visit is required to fully assess the reaction. Investigational sites will be alerted of any Grade 3 or higher (eg, ER visit or hospitalization) solicited systemic reactions, which will require discontinuation of vaccinations upon verification by the PI or designee of the Grade 3 or higher status. The PI or designee may require participants reporting Grade 3 or higher reactions to return to the clinic for an unscheduled visit to aid in this evaluation.

In addition to any reaction considered an AE by the PI, solicited reactions reported in the e-diary will be recorded by the PI or designee on the AE eCRF if they are serious [ie, a solicited reaction will be considered ‘serious’ if confirmed by the investigator to be a Grade 4, or a Grade 3 that upon the investigator’s assessment meets any of the SAE criteria outlined in [Section 9.1.2](#)]; result in discontinuation of study product or withdrawal from the study; or remain unresolved for 14 days or more. Solicited systemic reactions may require discontinuation of vaccinations based on individual participant halting rules (see [Section 7.3](#)).

The rating scale to be used for reactogenicity events is the same toxicity grading scale provided in [Appendix A](#), the FDA Guidance for Industry: *Toxicity Grading Scale for Healthy Adult and Adolescent Volunteers Enrolled in Preventive Vaccine Clinical Trials* {[CBER, 2007](#)}, where symptoms are assessed as Grade 1=mild through Grade 4=potentially life-threatening. Additionally, a Grade of 0 will be available in the e-diary in order to allow the participant to record “symptom not present.” For most of the reactogenicity events, there is a direct

corresponding symptom entry in the toxicity grading scale (eg, for systemic reactions: fever, headache, fatigue, myalgia; for local reactions: pain, tenderness, erythema/redness, induration/swelling) – refer to [Table 8](#).

For reactogenicity events with no direct corresponding symptom entry in [Table 8](#) (eg, warmth, itching, arm motion limitation, bruising), the grading for “illness or clinical AE” will be used to rate the symptom severity. The symptom-severity descriptions in [Table 8](#) will be translated to lay language in the e-diary instrument to promote participant understanding.

Participants will receive the measuring implements – oral thermometer and injection site reaction measurement tool – at the Day 1 visit, along with use instructions. Oral temperature (°F) will be recorded daily (at least once a day) by the participant in the e-diary. Using the injection site measurement tool, the participant will measure redness and/or swelling at the injection site and then grade these accordingly [ie, redness grade is based on greater of the two perpendicular measurements in centimeters, while swelling grade is based on greater of the two perpendicular measurements in centimeters and the functional scale (if applicable); see [Table 8](#)] in the e-diary. The PI may request the participant to attend an unscheduled study visit to evaluate any symptoms recorded in the e-diary.

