17. APPENDICES

APPENDIX A. TOXICITY GRADING SCALE FOR HEALTHY ADULT AND ADOLESCENT VOLUNTEERS ENROLLED IN PREVENTIVE VACCINE CLINICAL TRIALS

The toxicity grading scale that will be used to rate the severity of local reaction to injectable product, vital signs, and general systemic condition related to clinical abnormality and laboratory abnormality are presented in [Table 8](#) and [Table 9](#), respectively (based on the FDA Guidance for Industry: *Toxicity Grading Scale for Healthy Adult and Adolescent Volunteers Enrolled in Preventive Vaccine Clinical Trials* {[CBER, 2007](#)}).

Table 8: Toxicity Grading Scale for Clinical Abnormalities in Healthy Adult and Adolescent Volunteers

Toxicity	Grade 1 (Mild)	Grade 2 (Moderate)	Grade 3 (Severe)	Grade 4 (Potential Life-Threatening)
Local Reaction to Injectable Product				
Pain	Does not interfere with activity	Repeated use of non-narcotic pain reliever >24 hours or interferes with activity	Any use of narcotic pain reliever or prevents daily activity	ER visit or hospitalization
Tenderness	Mild discomfort to touch	Discomfort with movement	Significant discomfort at rest	ER visit or hospitalization
Erythema/redness ^a	2.5–5 cm	5.1–10 cm	>10 cm	Necrosis or exfoliative dermatitis
Induration/swelling ^b	2.5–5 cm and does not interfere with activity	5.1–10 cm or interferes with activity	>10 cm or prevents daily activity	Necrosis
Vital Signs^c				
Fever (°C) (°F) ^d	38.0–38.4 100.4–101.1	38.5–38.9 101.2–102.0	39.0–40 102.1–104	>40 >104
Tachycardia (beats/minute)	101–115	116–130	>130	ER visit or hospitalization for arrhythmia
Bradycardia ^e (beats/min)	50–54	45–49	<45	ER visit or hospitalization for arrhythmia
Hypertension – systolic (mmHg)	141–150	151–155	>155	ER visit or hospitalization for malignant hypertension
Hypertension – diastolic (mmHg)	91–95	96–100	>100	ER visit or hospitalization for malignant hypertension

Toxicity	Grade 1 (Mild)	Grade 2 (Moderate)	Grade 3 (Severe)	Grade 4 (Potential Life-Threatening)
Hypotension – systolic (mmHg)	85–89	80–84	<80	ER visit or hospitalization for hypotensive shock
Respiratory rate (breaths/minute)	17–20	21–25	>25	Intubation
Systemic (General)				
Nausea/vomiting	No interference with activity or 1–2 episodes per 24 hours	Some interference with activity or >2 episodes per 24 hours	Prevents daily activity, requires outpatient IV hydration	ER visit or hospitalization for hypotensive shock

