Diarrhea	2–3 loose stools or <400 g per 24 hours	4–5 stools or 400–800 g per 24 hours	≥ 6 watery stools or >800 g per 24 hours or requires outpatient IV hydration	ER visit or hospitalization
Headache	No interference with activity	Repeated use of non-narcotic pain reliever >24 hours or some interference with activity	Significant; any use of narcotic pain reliever or prevents daily activity	ER visit or hospitalization
Fatigue	No interference with activity	Some interference with activity	Significant; prevents daily activity	ER visit or hospitalization
Myalgia	No interference with activity	Some interference with activity	Significant; prevents daily activity	ER visit or hospitalization
Illness or clinical AE ^f	No interference with activity	Some interference with activity not requiring medical intervention	Prevents daily activity and requires medical intervention	ER visit or hospitalization

AE = adverse event; ER = emergency room; IV = intravenous.

a In addition to grading the measured local reaction at the greatest single diameter, the measurement is recorded as a continuous variable.

b Swelling is evaluated and graded using the functional scale as well as the actual measurement. Induration is graded using the functional scale.

c Participant will be at rest for all vital sign measurements.

d Oral temperature; no recent hot or cold beverages or smoking.

e When resting heart rate is between 60–100 beats per minute. Clinical judgment will be used when characterizing bradycardia among some healthy subject populations, for example, conditioned athletes.

f Adverse event defined according to applicable regulations.

Table 9: Table for Laboratory Abnormalities

Panel and Analyte ^a	Mild (Grade 1)	Moderate (Grade 2)	Severe (Grade 3)	Potentially Life Threatening (Grade 4) ^b
Serum Chemistry				
Glucose – hypoglycemia (mg/dL)	65–69	55–64	45–54	<45
Glucose – hyperglycemia Fasting (mg/dL) Random (mg/dL)	100–110 110–125	111–125 126–200	>125 >200	Insulin requirements or hyperosmolar coma
Blood Urea Nitrogen (mg/dL)	23–26	27–31	>31	Requires dialysis
Creatinine (mg/dL)	1.5–1.7	1.8–2.0	2.1–2.5	>2.5 or requires dialysis
Alkaline phosphate increase by factor	1.1–2.0 x ULN	2.1–3.0 x ULN	3.1–10 x ULN	>10 x ULN
Liver Function Tests: ALT, AST increase by factor	1.1–2.5 x ULN	2.6–5.0 x ULN	5.1–10 x ULN	>10 x ULN
Bilirubin (when accompanied by any increase in Liver Function Test) increase by factor	1.1–1.25 x ULN	1.26–1.5 x ULN	1.51–1.75 x ULN	>1.75 x ULN

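### The example e-diary wording for Grade 3 (a symptom that needs treatment) contradicts Table 8, the scale that the same protocol section says the e-diary will use

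*Protocol*

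**What the plan says.** Protocol 8.3.5.1 has participants grade each solicited reaction in the e-diary and gives sample instructions. The Grade 3 sample reads "Grade 3 (Severe) = symptom prevents activities of daily living or requires treatment", and SAP 2.2.3.5 repeats it. The sample is introduced as an example and stops at Grade 3. Neither document defines treatment in this context.

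Later in 8.3.5.1 the protocol states: "The rating scale to be used for reactogenicity events is the same toxicity grading scale provided in" Appendix A, "where symptoms are assessed as Grade 1=mild through Grade 4=potentially life-threatening". It assigns warmth, itching, arm motion limitation and bruising to the generic row for illness or clinical AE. It adds that the Table 8 descriptions "will be translated to lay language in the e-diary instrument to promote participant understanding".

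Table 8 grades pain as Grade 2 for "Repeated use of non-narcotic pain reliever >24 hours or interferes with activity" and Grade 3 for "Any use of narcotic pain reliever or prevents daily activity". For headache, Grade 2 is "Repeated use of non-narcotic pain reliever >24 hours or some interference with activity", and Grade 3 again turns on narcotic use or prevented activity. Fatigue and myalgia are graded on interference with activity alone up to Grade 3. Tenderness rises from discomfort on touch, to discomfort on movement, to "Significant discomfort at rest". Under footnote b, induration is graded on the functional scale. On the generic row, Grade 3 needs prevented activity together with medical intervention.

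Solicited reactions by severity, as participants report them in the e-diary, are a secondary safety endpoint (protocol 3.2.2, SAP 2.3.2). Under Table 5, item 2, a Grade 3 or higher systemic e-diary symptom, once the investigator confirms it, ends vaccination for that participant.

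**The concern.** A lay translation of a scale has to keep the scale's cut-points. The example does not, because it adds a route to Grade 3 through treatment alone, joined by *or*, that Table 8 does not have. One protocol section therefore gives two incompatible thresholds for the same entry, and the SAP repeats one of them.

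Two things depend on the grade. The first is the severity distribution in the e-diary tables (protocol 10.6.7.1, SAP 7.7.1), which a reader would take to be on the Table 8 scale that both documents name. The second is the set of systemic entries that arrive as Grade 3 or higher and so go to the investigator for confirmation.

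Treated reactions are foreseeable. Protocol 2.2.3 says that earlier reactions of these kinds often resolved either untreated or with NSAIDs used to treat the more severe or prolonged symptoms. The protocol's own usage therefore does not exclude an over-the-counter analgesic from being treatment.

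**Working it through.** The plan states no figure to reproduce. The check sets the two texts side by side.

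**Symptoms exposed.** The e-diary solicits 9 injection-site and 4 systemic reactions, 9 + 4 = 13. Fever is graded by program from temperature, and redness and swelling mainly from measurement. That leaves 13 − 3 = 10 graded on words: pain, tenderness, induration, warmth, itching, arm motion limitation, bruising, tiredness, muscle ache and headache. The last 3 are systemic, so Table 5, item 2 applies to them.

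**Grade by grade.** Take a reaction that meets the treatment criterion but does not prevent activity. The example wording gives Grade 3 throughout. Difference = example grade − Table 8 grade.

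| Reaction | Example | Table 8 | Difference |
|---|---|---|---|
| Pain or headache, non-narcotic used repeatedly beyond 24 hours | 3 | 2 | 1 |
| Pain or headache, one non-narcotic dose, no interference | 3 | 1 | 2 |
| Fatigue or myalgia, some interference | 3 | 2 | 1 |
| Fatigue or myalgia, no interference | 3 | 1 | 2 |
| Tenderness on movement | 3 | 2 | 1 |
| Mild tenderness on touch | 3 | 1 | 2 |
| Induration that interferes with activity | 3 | 2 | 1 |
| Induration that does not interfere | 3 | 1 | 2 |
| Generic row, no interference | 3 | 1 | 2 |
| Pain or headache, narcotic used | 3 | 3 | 0 |

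The last row shows that the conflict is not universal: where a narcotic is used, the texts agree.

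**Sensitivity to the meaning of treatment.** If it includes self-medication, every row can arise. If it means only treatment ordered by a clinician, the self-medicated analgesic cases drop out. Three conflicts remain: a prescribed non-narcotic for pain or headache; treated fatigue, myalgia, tenderness or induration; and *or* against *and* on the generic row. The contradiction therefore survives the narrow reading, with fewer cases.

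**Numbers affected.** The documents give no rate of treated reactions that leave activity intact, so no count or percentage can be derived. The differences above are per event and are not an effect size.

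**The case against.** The best defense is that the protocol has one governing scale and a loose illustration. The bracketed text is marked as an example, omits Grade 4 and ignores the measured reactions, so it cannot be the whole instrument. The operative sentences name Appendix A. The e-diary also asks about pain and fever medication as a separate yes/no item, which suggests that self-medication was not meant to drive the grade. Much of this stands: the instrument may well follow Table 8, and the harm is conditional. It does not remove the contradiction. The example is the only participant grading text shown for these symptoms, it appears in both documents, and no passage excludes self-medication.

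A reader might infer more than the documents support:

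- *The investigator has two standards to confirm against.* The example describes what the participant is prompted with. Protocol 8.3.5.1, protocol 9.2.1 and SAP 3.8 all point to Appendix A for grading, so the investigator has one named scale. The exposure lies in which entries are sent for confirmation.
- *Some reactions have no Table 8 grade because of this wording.* Some interference plus medical intervention does fall between Grades 2 and 3 on the generic row, but that gap is inside Table 8 and exists whatever the example says.
- *The endpoint has no settled grader.* SAP 3.8 does say that the investigator or designee assesses the severity of reactogenicity events, in a paragraph that also mentions the e-diary. But SAP 2.2.3.5 has the participant grade, SAP 2.3.2 defines the endpoint from participant e-diaries, and SAP 7.7.1 tabulates e-diary data. The SAP 3.8 sentence is loose drafting that could fit in-clinic reactions (SAP 7.7.2) or reactions entered on the AE form.
- *The comparison between vaccines is biased.* Nothing shows that the wording would act differently by group, and the summaries are descriptive.

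**Conclusion.** The contradiction is real and should be corrected. The example Grade 3 anchor in protocol 8.3.5.1 and SAP 2.2.3.5 is not a translation of Table 8. For a treated reaction that does not prevent activity, it gives a grade one or two higher, across the 10 of 13 solicited symptoms graded on words, except where a narcotic is used for pain or headache.

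The consequence is conditional on the e-diary carrying the example wording. If it does, the severity tables for this secondary safety endpoint are not on the scale that the protocol and SAP name, and more systemic entries may go forward for confirmation under Table 5, item 2. If the e-diary follows Table 8, the fault is confined to the text. The documents do not settle which is the case. No view is taken on which anchor or clinical rule is right.

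**What to change.** 1. Reconcile the sample wording in protocol 8.3.5.1 and SAP 2.2.3.5 with Table 8, so that the e-diary, the severity tables and the Table 5, item 2 confirmation share one set of anchors. If the term treatment is kept, define it, including whether self-medication counts.
2. Check the wording that the e-diary actually used. If it was the example text, say so in the severity tables and do not present those grades as Table 8 grades.
3. Do not change the e-diary anchors partway without a flag. SAP Appendix IV already describes participants who had received all three vaccinations, so a change now could put two scales into one endpoint.
4. As a minor consistency edit, limit the SAP 3.8 sentence on investigator grading of reactogenicity so that it agrees with the participant-reported endpoint.

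The cost is wording in three sections (protocol 8.3.5.1, SAP 2.2.3.5 and SAP 3.8), one check of the instrument and possibly a table footnote. Revising the e-diary itself would also need its text re-approved and entries made under the old wording flagged.

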3.2. Study Endpoints

3.2.1. Primary Endpoints

The primary study endpoints are as follows:

Lot Consistency:

- Equivalent immunogenicity across three consecutive AV7909 lots as demonstrated by the 95% CI for the ratios of geometric mean TNA NF₅₀ at Day 64 for each of the three lot-to-lot comparisons to be within 0.5 and 2.0.
- Protective level of immunogenicity in all three consecutive AV7909 lots as demonstrated by the LB of the two-sided 95% CI to be $\geq 40\%$ for the proportions of AV7909 subjects in each of the three lots achieving a TNA NF₅₀ ≥ 0.56 at Day 64.

Immunogenicity:

- Lower bound of the two-sided 95% CI is $\geq 40\%$ for the proportion of AV7909 participants in Groups 1-3 (three lots pooled) achieving a TNA NF₅₀ ≥ 0.56 on Day 64.

- Non-inferiority of AV7909 to BioThrax at Day 64 as determined by the two-sided lower 95% CI of the difference in the proportion of AV7909 participants (three lots pooled) with a TNA NF₅₀ ≥ 0.29 and the proportion of BioThrax participants with a TNA NF₅₀ ≥ 0.29 being greater than -15%.

Safety:

- Incidences of SAEs from the time of the first vaccination on Day 1 through the 12-month safety follow-up telephone call following the last vaccination.

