9.1.2. Serious Adverse Event

A serious AE (SAE) is any untoward medical occurrence at any dose that fulfils one or more of the following:

- Results in death
- Is life-threatening, eg, the participant was, in the opinion of the investigator, at immediate risk of death from the event as it occurred (does not include an event that, had it occurred in a more severe form, might have caused death)
- Requires inpatient hospitalization or prolongation of existing hospitalization. (Note: a prescheduled hospitalization is not considered an SAE.)
- Results in persistent or significant disability or incapacity
- Is a congenital anomaly or birth defect
- Is an other medically significant event that, based upon appropriate medical judgment, may jeopardize the participant and may require medical or surgical intervention to prevent one of the outcomes listed above (eg, allergic bronchospasm requiring intensive treatment in an emergency room or home, blood dyscrasias or convulsions that do not result in hospitalization, the development of drug dependency or drug abuse)

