2.2.3.5 E-Diary Reactogenicity

Reactogenicity (solicited systemic and injection site reactions) will be monitored by study site personnel for 30 minutes after vaccination and thereafter assessed daily by the

participants using e-diaries, starting on the evening after each vaccination, for at least seven days. If injection site or systemic reactions continue beyond seven days, participants will be prompted to continue diary entries until they are symptom-free for two consecutive days.

In the e-diary, information will be solicited on the following injection site reactions: warmth, tenderness, itching, pain, arm motion limitation, redness, induration, swelling, and bruising. In addition, information will be solicited on the following systemic reactions: tiredness, muscle ache, headache, and fever (oral temperature). The participant will be prompted to grade the severity of each reaction according to the instructions provided [e.g., Grade 0 (Absent)= symptom not present; Grade 1 (Mild) = symptom present but does not interfere with activities of daily living; Grade 2 (Moderate) = symptom causes some interference with activities of daily living; Grade 3 (Severe) = symptom prevents activities of daily living or requires treatment)].

Oral temperature (°F) will be recorded daily (at least once a day) by the participant in the e-diary.

Participants will also be asked to respond (yes/no) if they have taken pain/fever medications such as acetaminophen, aspirin, and nonsteroidal anti-inflammatory drugs (NSAIDs; e.g., ibuprofen) or other medication in the past 24 hours. Use of such medications recorded in the e-diary must be confirmed with the participant and recorded in the eCRF.

In addition to any reaction considered an AE by the PI, solicited reactions reported in the e-diary will be recorded by the PI or designee on the AE eCRF if they are serious [i.e., a solicited reaction will be considered ‘serious’ if confirmed by the investigator to be a Grade 4, or a Grade 3 that upon the investigator’s assessment meets any of the SAE criteria outlined in [Protocol EBS.AVA.212, Section 9.1.2](#)]; result in discontinuation of study product or withdrawal from the study; or remain unresolved for 14 days or more.

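### Confirmed Grade 4 solicited reactions are serious by grade alone, so the primary SAE endpoint can include events that are not SAEs under Protocol 9.1.2

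*Protocol*

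**What the plan says.** Protocol 8.3.5.1 lists when a solicited e-diary reaction must go on the AE eCRF, and one ground is that it is serious. The bracketed definition opens with the words "if confirmed by the investigator to be a Grade 4, or a Grade 3 that upon the". What follows makes the Grade 3 limb, but not the Grade 4 limb, depend on a Section 9.1.2 criterion. SAP 2.2.3.5 carries the same rule ("if confirmed by the investigator to be a Grade 4, or a Grade 3 that upon", and so on).

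Protocol 9.1.2 says an SAE "is any untoward medical occurrence at any dose that fulfils one or more of the following", and then lists outcomes: death, immediate risk of death, inpatient admission, disability, congenital anomaly, or medical significance on medical judgment. The life-threatening criterion "does not include an event that, had it occurred in a more severe form, might have caused death". The hospital criterion is "Requires inpatient hospitalization or prolongation of existing hospitalization".

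In Appendix A, Table 8, Grade 4 is "ER visit or hospitalization" for pain, tenderness, headache, fatigue, myalgia and the generic illness row. For fever it is a reading above 104 °F. Section 8.3.5.1 assigns warmth, itching, arm motion limitation and bruising to the generic row.

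The only primary safety endpoint (Protocol 3.2.1) is "Incidences of SAEs from the time of the first vaccination on Day 1 through the 12-month safety follow-up" call. SAP 7.2.3 analyses it as the proportion of participants with serious TEAEs, with exact confidence intervals and a relative risk of AV7909 to BioThrax, and plans no hypothesis test.

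**The concern.** Severity and seriousness are different attributes, and the Grade 4 limb uses one in place of the other. A reaction on the e-diary list can become serious because of its grade. An unsolicited event graded on the same Table 8 row becomes serious only through 9.1.2. Two seriousness rules then feed one count, and that count is the primary safety measure.

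The solicited symptoms are the ones most likely to depend on the product. They could differ between arms because of the added adjuvant and the different injection routes. If enough Grade 4-only reactions occurred, the SAE rate, the vaccine-related SAE rate and the relative risk would partly reflect reactogenicity. BioThrax has only 550 participants, so a few reclassified participants there would move the ratio visibly.

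**Working it through.** **1. The plan's own safety figure.** Protocol 10.1 gives a 95% chance of seeing at least one event with a true rate of 0.1% in 3000 AV7909 participants. The formula is 1 − (1 − 0.001)^n. For n = 3000 it gives 95.03%; for n = 2970 (3300 × 0.90) it gives 94.88%. The figure reproduces and does not depend on how an SAE is defined.

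**2. The two rules side by side.**

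| Event | 8.3.5.1 / SAP 2.2.3.5 | 9.1.2 |
|---|---|---|
| Solicited headache or itching, ER visit, no admission (Grade 4) | Serious | Only if judged medically significant |
| Solicited fever above 104 °F, no complication (Grade 4) | Serious | Only if judged medically significant |
| Solicited headache, inpatient admission (Grade 4) | Serious | Serious |
| Solicited Grade 3 reaction | Serious if it meets 9.1.2 | Same |
| Unsolicited illness, ER visit, no admission (Grade 4) | Rule does not apply | Only if judged medically significant |

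The conflict is confined to the first two rows. The last row shows the same grade handled differently because the symptom is not on the e-diary list.

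**3. Route to the endpoint.** A solicited reaction that is serious under 8.3.5.1 is recorded on the AE eCRF. Starting after the first vaccination, it is a TEAE, and SAP 7.2.3 counts participants with serious TEAEs. Neither document says whether a Grade 4 reaction meeting no 9.1.2 criterion is in that count.

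**4. Size, as an illustration only.** The documents give no expected SAE rate and no rate of Grade 4 reactions that fail 9.1.2. Both are assumed here. Let s be the SAE rate under 9.1.2, the same in both arms, and gA and gB the added Grade 4-only rates in AV7909 and BioThrax. The randomised numbers are 3300 and 550.

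- Count in an arm = N × (s + g).
- Relative risk = (s + gA) / (s + gB).

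With s = 1% and equal added rates of 0.05% to 0.5%:

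- AV7909 goes from 33 to between 3300 × 0.0105 = 34.7 and 3300 × 0.015 = 49.5.
- BioThrax goes from 5.5 to between 550 × 0.0105 = 5.8 and 550 × 0.015 = 8.25.
- The relative risk stays at 1.00.

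With unequal added rates:

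| s (assumed) | gA = 0.5%, gB = 0.1% | gA = 0.1%, gB = 0.5% |
|---|---|---|
| 0.5% | 1.0/0.6 = 1.67 | 0.6/1.0 = 0.60 |
| 1.0% | 1.5/1.1 = 1.36 | 1.1/1.5 = 0.73 |
| 2.0% | 2.5/2.1 = 1.19 | 2.1/2.5 = 0.84 |

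At s = 1%, two reclassified BioThrax participants alone would give (33/3300) / (7.5/550) = 0.73. These calculations assume that every added reaction fails 9.1.2 and that no affected participant already has another SAE, so for the rates assumed they overstate the number added.

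**The case against.** The rule is explicit, prespecified, identical in both documents and applied under blinding in both arms. Treating confirmed reactions in the potentially life-threatening column as serious is a conservative convention. Many Grade 4 reactions would also meet 9.1.2: an inpatient admission does so directly, and necrosis or exfoliative dermatitis may do so on medical judgment. The medical-significance criterion itself gives intensive emergency-room treatment as an example, and the investigator must confirm the grade. SAEs and Grade 3 or 4 TEAEs are listed and solicited reactions are tabulated by grade, so the affected cases could be found afterwards. All of this stands and narrows the point. It does not settle which definition sets the flag used in SAP 7.2.3.

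A reader might infer more than the documents support:

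- **That solicited reactions are classified by grade throughout.** They are not: the Grade 3 limb applies 9.1.2 in terms.
- **That a hospitalised participant with a Grade 1 or 2 reaction would be missed.** The bracket does omit those grades, but this is only a wording gap. Section 9.1.2 has no grade limit, 9.3.1 requires any SAE to be reported, 9.2 resolves doubt in favour of recording, and 8.3.5.1 lets the investigator record any reaction as an AE.
- **That the SAE count is inflated by some known percentage, or the relative risk biased in a known direction.** Every rate above is assumed. Protocol 4.3 reports more frequent and more severe injection-site reactions when CPG 7909 was added in Study V011. It also anticipates less reactogenicity IM than SC, and describes the selected formulation's injection-site reactogenicity as similar to BioThrax.

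**Conclusion.** The inconsistency is established from the text alone. A confirmed Grade 4 solicited reaction is serious under Protocol 8.3.5.1 and SAP 2.2.3.5 without any 9.1.2 criterion, and it can enter the primary safety count. The events at issue are narrow: mainly ER visits without admission, or fever above 104 °F alone, that the investigator does not judge medically significant.

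The size and direction of the effect on the SAE rate and relative risk cannot be derived from the documents. The range of 0.60 to 1.67 above rests wholly on assumed rates, and equal added rates with equal background rates leave the ratio at 1.00. The endpoint is estimated, not tested, so no alpha or power figure changes. It is worth correcting because it concerns the definition of the only primary safety endpoint and the analysis change is small.

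**What to change.** 1. **Reconcile Protocol 8.3.5.1 and 9.1.2 with SAP 2.2.3.5**, so that sites and programmers work from one statement of seriousness. This is more than a label. Section 9.3.1 ties immediate reporting to SAE status, and Table 5 item 11 ties vaccination discontinuation to a causally related SAE. Item 2 covers systemic reactions and item 10 unsolicited AEs, so for a Grade 4 local reaction the serious label may be what brings item 11 into play. The sponsor should check both consequences. This review does not say which clinical rule is right.

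2. **In SAP 7.2.3, state which definition sets the seriousness flag.** Base the primary SAE incidence and relative risk on events meeting at least one 9.1.2 criterion. Show separately, by arm, the solicited reactions that are serious only because they are Grade 4.

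The second change costs one extra table row and a record of which 9.1.2 criterion each serious event met. It need not await the first, and all confirmed Grade 4 solicited reactions stay on the AE eCRF.
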